9.2 Background Characteristics

9.2.1 Subject Disposition

The number and percentage of subjects in the following categories will be summarized:

- All Subjects Set (Number only)

Ivacaftor Run-in Period:

- Dosed (Safety Set) in the Ivacaftor Run-in Period
- Completed treatment in the Ivacaftor Run-in Period
- Prematurely discontinued treatment during the Ivacaftor Run-in period and the reasons for treatment discontinuation

Active Comparator Treatment Period:

- Randomized in the Active Comparator Treatment Period (Number only)

- Dosed in the Active Comparator Treatment Period (Number only)
- FAS (randomized, dosed, and with the intended CFTR allele mutation in the Active Comparator Treatment Period; Number only)
- Completed treatment in the Active Comparator Treatment Period
- Prematurely discontinued treatment during the Active Comparator Treatment Period and the reasons for treatment discontinuation
- Completed the study or the Safety Follow-up Visit
- Prematurely discontinued the study, and the reasons for discontinuation, by the following subcategories:
 - Discontinued the study during the Active Comparator Treatment Period
 - Discontinued the study after the Active Comparator Treatment Period
- Last scheduled visit completed for everyone in FAS

For categories related to the Ivacaftor Run-in Period, the number and percentage of subjects in each disposition category will be summarized, with the number in the safety set in the Ivacaftor Run-in Period as the denominator, together with the number of subjects enrolled but never dosed. A listing will be provided for subjects who discontinued treatment during the Ivacaftor Run-in Period or who discontinued the study during the Ivacaftor Run-in Period with the reasons for discontinuation.

The number and percentage of enrolled subjects in the Ivacaftor Run-in Period will be summarized overall using the number of subjects in the All Subjects Set as the denominator. An enrollment listing will be provided, with subjects enrolled ordered by the enrollment date.

For the categories related to the Active Comparator Treatment Period, the number and percentage of subjects in each disposition category will be summarized, with the number of subjects in the FAS as the denominator, except as noted above.

The number and percentage of randomized subjects in the Active Comparator Treatment Period will be summarized by stratification factors, and by country and by site, using the Active Comparator Subjects Set. A randomization listing will be provided with subjects ordered by randomization date.

A listing will be provided for subjects who discontinued treatment during the Active Comparator Treatment Period or who discontinued study during the Active Comparator Treatment period with the reasons for discontinuation.

9.2.2 Demographics and Baseline Characteristics

Demographics, medical history and baseline characteristics will be summarized overall based on the Safety Set in the Ivacaftor Run-in Period and on the FAS by randomized treatment group in the Active Comparator Treatment Period.

Demographic data will include the following:

- Age (in years)

- Age groups at the Screening visit (<18 versus ≥ 18 years of age)
- Sex
- Ethnicity (Hispanic or Latino, not Hispanic or Latino, and not collected per local regulations)
- Race (White, Black or African American, Asian, American Indian or Alaska Native, Native Hawaiian or Other Pacific Islander, and Other)
- Geographic region (North America, Europe, Australia)

Baseline characteristics will include the following:

- Type of mutation in the second *CFTR* allele (R117H, Others)
- Weight (kg)
- Height (cm)
- BMI (kg/m^2)
- Weight z-score (subjects <20 years old)
- Height z-score (subjects <20 years old)
- BMI z-score (subjects <20 years old)
- type of mutation on the second *CFTR* allele (*R117H* versus other allowed mutations)

Disease characteristics will include the following:

- Percent predicted FEV₁ at screening (<70, ≥ 70 ; for Ivacaftor Run-in Period)
- Percent predicted FEV₁ at baseline (<40, ≥ 40 to <70, ≥ 70 to ≤ 90 , >90; for Active Comparator Treatment Period)
- Percent predicted FEV₁ at baseline
- FEV₁ (L)
- FVC (L)
- Percent predicted FVC
- FEF_{25-75%} (L/sec)
- Percent predicted FEF_{25-75%}
- FEV₁/FVC
- Sweat Chloride
- CFQ-R respiratory domain
- Received dornase alfa before first dose of study drug (Yes, No)
- Received any inhaled antibiotic before first dose of study drug (Yes, No)
- Received any bronchodilator before first dose of study drug (Yes, No)

Note: On the bronchodilator page, only those coded as bronchodilator will be included.

- Received any inhaled bronchodilator before first dose of study drug (Yes, No)

Note: On the bronchodilator page, only those coded as bronchodilator will be included.

- Received any inhaled hypertonic saline before first dose of study drug (Yes, No)
- Received any inhaled corticosteroids before first dose of study drug (Yes, No)
- Colonization of *Pseudomonas aeruginosa* status before the Ivacaftor Run-in Period (Positive, Negative)

Subjects with exclusionary liver function test results at screening could be retested once within 14 days and were considered eligible if these repeated results met eligibility criteria. Two summaries will be provided: one for the initial liver function testing test only; and one based on the retesting results (if available).

9.2.3 Medical History

Medical history will be coded by using the Medical Dictionary for Regulatory Activities (MedDRA) and will be summarized descriptively using the FAS population. Medical history will be summarized descriptively by system organ class (SOC) and preferred term (PT). In addition, the number of subjects reported to have had positive cultures for respiratory pathogens in the 2 years prior to screening (i.e., answered yes on the respiratory microbiology form) will be summarized by test and subcategories within the test. Hospitalization and clinic visit history in the past year will be listed.

9.2.4 Prior and Concomitant Medications

Medication use will be coded using the World Health Organization-Drug Dictionary Enhanced and categorized as:

- **Prior medication:** any medication that started before initial dosing of study drug in the Ivacaftor Run-in Period, regardless of when it ended.
- **Concomitant medication during the Ivacaftor Run-in Period:** medication that continued or that started at or after the first dose of study drug through the end of the TE Period for the Ivacaftor Run-in Period.
- **Concomitant medication during the Active Comparator Treatment Period:** medication that continued or that started at or after the first dose of study drug through the end of the TE Period of the Active Comparator Treatment Period.
- **Post-treatment medication:** medication that continued or that started after the end of the TE Period of the Active Comparator Treatment Period.

A given medication can be classified as a prior medication, a concomitant medication (concomitant medication during the Ivacaftor Run-in Period and/or a concomitant medication during the Active Comparator Treatment Period), or a post-treatment medication; both prior and concomitant; both concomitant and post-treatment; or prior, concomitant, and posttreatment. If a medication has a missing or partially missing start/end date or time and it

cannot be determined whether it was taken before initial dosing, concomitantly, or beyond the TE Period, it will be considered as prior, concomitant, and post-treatment.

Prior medications and concomitant medications in the Ivacaftor Run-in Period will be summarized descriptively based on the Safety Set in that period.

Prior medications and concomitant medication in the Ivacaftor Run-in Period also will be summarized descriptively based on the FAS for the Active Comparator Treatment Period. Concomitant medications in the Active Comparator Treatment Period also will be summarized descriptively based on the FAS.

Post-treatment medications will be listed for each subject.

Details for imputing missing or partial start and/or stop dates of medication are described in [Appendix E](#).

9.2.5 Study Drug Exposure

Duration of study drug exposure (in days) will be calculated as: last dose date – first dose date + 1 day, regardless of study drug interruption.

Exposure will be summarized separated for the Ivacaftor Run-in Period and the Active Comparator Treatment Period based on the corresponding safety set.

9.2.6 Study Drug Compliance

Study drug compliance based on study drug exposure will be calculated as: $100 \times [1 - (\text{total number of days of any study drug interruption}) / (\text{duration of study drug exposure in days})]$.

Study drug compliance will be summarized descriptively by the number of subjects (n), mean, SD, SE, median, min, and max. Compliance also will be summarized in categories: <80% and $\geq 80\%$ using frequency tables.

Study drug compliance will be summarized for the Ivacaftor Run-in Period based on the Ivacaftor Run-in Period Safety Set, and for the Active Comparator Treatment period based on the FAS.

9.2.7 Important Protocol Deviations

Important protocol deviations (IPD) are a subset of protocol deviations that may significantly impact the completeness, accuracy, and/or reliability of the study data or that may significantly affect a subject's rights, safety, or well-being. IPD rules will be developed and finalized before database lock.

The protocol deviations that should be considered as potential IPDs include, but are not limited to:

- Violation of subjects rights, safety or well-being
- Subject entered the study despite violation of any inclusion or exclusion criteria
- Subject was less than 80% compliant with study medications
- Subject received excluded concomitant medications

- Subject received the wrong treatment or incorrect doses
- Subject remained in study despite meeting withdrawal criteria

Occurrence of any of these events should be considered as potential IPDs, but the blinded team should categorize them as IPDs only if they have the potential to affect interpretation of study results.

IPDs (from the clinical database or from the site deviation log) will be summarized descriptively and presented in an individual subject data listing.

9.3 Efficacy Analysis

All efficacy analyses described in this section will be based on the FAS during the Active Comparator Treatment Period, unless specified otherwise. The analysis will include all available measurements through the last assessment, including measurements after treatment discontinuation, per the visit windowing rules described in [Appendix D](#).

Summary statistics may be provided for efficacy endpoints during the Ivacaftor Run-in Period.

9.3.1 Analysis of Primary Efficacy Endpoint(s)

9.3.1.1 Definition

The primary efficacy endpoint is the average absolute change from baseline in percent predicted FEV₁ (with a unit of percentage points) through Week 8 in the Active Comparator Treatment Period.

Percent predicted FEV₁ is the ratio of FEV₁ (L) to the predicted FEV₁ (L), expressed as a percentage. The predicted FEV₁ will be calculated using the Hankinson¹ and Wang² standards with details in [Appendix F](#).

9.3.1.2 Summary in Ivacaftor Run-in Period

Percent predicted FEV₁, both the raw values and their absolute change from baseline, will be summarized by visit for the Ivacaftor Run-in Period (Week -4, Week -2 and Day 1 predose).

9.3.1.3 Primary Analysis

The primary analysis for the primary efficacy endpoint will be based on a mixed model for repeated measures (MMRM) using SAS PROC MIXED in the FAS for the Active comparator Treatment Period. The null hypothesis to be tested is that the average absolute change from baseline in percent predicted FEV₁ through Week 8 is the same for the two treatment arms. The MMRM will be used to test the difference between treatment groups. A *P* value of 0.05 or less will be interpreted as sufficient evidence to reject the null hypothesis.

The model will include absolute change from baseline in percent predicted FEV₁ (including all measurements up to Week 8 [inclusive], both on-treatment measurements and measurements after treatment discontinuation) as the dependent variable, treatment, visit (as a class variable), and treatment-by-visit interaction as fixed effects, with adjustment for age

group at screening (<18 versus \geq 18 years of age), type of mutation on the second *CFTR* allele (*R117H* versus Others), and baseline percent predicted FEV₁ value for the Active Comparator Treatment Period as fixed effects, and subject as a random effect. An unconstructed covariance structure will be used to model the within-subject errors.

A Kenward-Roger approximation will be used for the denominator degrees of freedom. If there is a convergence problem due to the unstructured covariance matrix, a compound symmetry covariance structure will be used to model the within-subject errors. No imputation of missing data will be done.

The primary result obtained from the model will be the average treatment effect through Week 8 in the Active Comparator Treatment Period. A contrast based on the fixed effects in the model will be used to estimate the average treatment effect across post-baseline visits through Week 8. The contrast will be constructed at the baseline covariate mean for the combined treatment groups using unique subjects in the FAS who have at least one post-baseline measurement through Week 8.

Descriptive summary statistics, including number of subjects, mean, standard deviation (SD), and LS means, standard error (SE), and 2-sided 95% confidence interval, along with the *P* value will be provided. In particular, the difference in LS means, SE, and the corresponding 2-sided 95% CI will be provided along with the *P* value to assess the average treatment difference between VX-661/ivacaftor combination therapy and Ivacaftor monotherapy through Week 8 in the Active Comparator Treatment Period. Additionally, the *P* value testing the treatment-by-visit interaction will be provided to assess the consistency of treatment effects across different visits.

In addition, the average raw values and average absolute change from baseline in percent predicted FEV₁ through Week 8 (Weeks 2, 4, and 8) will be summarized descriptively (number, mean, SD, SE, median, min, and max). In the raw value summaries, the average raw values through Week 8 will be derived as the arithmetic mean of the available postbaseline measurements at each visit. The average absolute change from baseline in percent predicted FEV₁ through Week 8 will be derived as the arithmetic mean of the absolute change from baseline in percent predicted FEV₁ at each available postbaseline visit.

The cumulative distribution plot of the average absolute change from baseline in percent predicted FEV₁ through Week 8 will be plotted by treatment group. Subjects missing absolute change from baseline in percent predicted FEV₁ at all post baseline visit through Week 8 will have missing average absolute change through Week 8 and will not be included in the related summaries or in the plot.

Absolute change from baseline in percent predicted FEV₁ at each visit

Absolute change from baseline in percent predicted FEV₁ at each postbaseline visit (Weeks 2, 4, and 8) during the Active Comparator Treatment Period will be derived from the main model based on the FAS. Descriptive summary statistics, including number of subjects, mean (SD), and LS means (SE), along with the corresponding 2-sided 95% CIs and the *P* values will be provided. In addition, the difference in LS means (SE) between VX-661/ivacaftor combination therapy and Ivacaftor monotherapy and the corresponding 95% CI will be provided. The LS means (95% CI) at each visit will be plotted by treatment groups.

In addition, the raw values and the absolute change from baseline in percent predicted FEV₁ at each postbaseline visit (Weeks 2, 4, and 8), regardless of the treatment status at the visit, will be summarized descriptively (number, mean, SD, SE, median, min, and max).

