### 12.3.3 Efficacy Analysis

#### 12.3.3.1 Analysis of Primary Variables

The primary efficacy endpoint is the absolute change in percent predicted FEV1 from baseline through Week 8 in the Active Comparator Treatment Period.

The primary analysis will be based on a mixed effects model for repeated measures (MMRM) with absolute change in percent predicted FEV1 from baseline at each time point through Week 8 in the Active Comparator Treatment Period as the outcome variable. The null hypothesis to be tested is that the mean absolute change in percent predicted FEV1 from baseline through Week 8 in the Active Comparator Treatment Period is the same for the 2 treatment arms. A *P* value of 0.05 or less will be interpreted as sufficient evidence to reject the null hypothesis.

The model will include the absolute change in percent predicted FEV1 from baseline at each visit (including all measurements up to Week 8 [inclusive]) as the dependent variables; treatment, visit, and treatment-by-visit interaction as fixed effects; and subject as a random effect. The model will also adjust for age group at the Screening Visit (<18 versus ≥18 years old), type of mutation on the second *CFTR* allele (*R117H* versus other allowed mutations; Section 16), and percent predicted FEV1 severity determined at the end of the Ivacaftor Run-in Period (<70 versus ≥70).

In the model, visit will be treated as a class variable, assuming an unstructured covariance structure to model the within-subject errors. This model imposes no assumptions on the correlational structure and is considered robust. If there is a convergence problem due to the unstructured covariance matrix, a compound symmetry covariance structure will be used to model the within-subject errors. Denominator degrees of freedom for the F-test for fixed effects will be estimated using the Kenward-Roger approximation. With a mixed-effects model as the primary analysis model based on restricted maximum likelihood estimation and assuming that, conditional on fixed and random effects, data are missing at random, no imputation of missing data will be performed.

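### The primary MMRM carries a redundant random subject effect, and its only fallback, compound symmetry, would miscalibrate the supportive per-visit results if variances differ by visit

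*SAP*

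**What the plan says.** SAP 9.3.1.3 puts two covariance terms in the primary model: "subject as a random effect. An unconstructed covariance structure will be used to model the within-subject errors". The adjective is evidently a slip for unstructured, because Protocol 12.3.3.1 has "assuming an unstructured covariance structure to model the within-subject errors". The Protocol also includes the random term: "treatment, visit, and treatment-by-visit interaction as fixed effects; and subject as a random effect".

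Both documents give one remedy for non-convergence. The SAP says "If there is a convergence problem due to the unstructured covariance matrix, a compound symmetry covariance structure will be used", and the Protocol says "a compound symmetry covariance structure will be used to model the within-subject errors". Neither lists an intermediate structure, an order of structures to try, or a robust standard error. On degrees of freedom the SAP says "A Kenward-Roger approximation will be used for the denominator degrees of freedom".

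The primary result is a contrast averaging the treatment effect over Weeks 2, 4 and 8. The same model also supplies the results at each visit: "Descriptive summary statistics, including number of subjects, mean (SD), and LS means (SE), along with the corresponding 2-sided 95% CIs", with P values. For the between-arm difference at a visit, SAP 9.3.1.3 promises a standard error and 95% CI, and Protocol 12.3.3.1 adds P values. Both report a treatment-by-visit P value. SAP 9.3.2.2 and 9.3.3.2 use similar models for relative change, CFQ-R and sweat chloride. The hierarchy in SAP 9.3.6 contains only averages through Week 8.

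**The concern.** An unstructured matrix for three visits leaves nothing for a subject variance to explain. Asking the software to estimate both can produce a boundary estimate, a Hessian that is not positive definite, or non-convergence. The plan would then move in one step from its most flexible structure to one that imposes a single variance and a single correlation. Protocol 12.3.3.1 defends the unstructured choice because it makes no assumption about the correlations, and the fallback gives that up.

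At stake are the per-visit intervals and P values. They are supportive, but Week 8 bears on durability of response, which Protocol 8.2.1 gives as the reason for the 8-week endpoint.

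**Working it through.** **Inputs from the documents.** Three post-baseline visits; 160 subjects 1:1, so 80 per arm, or 72 after 10% dropout; common SD 7; two-sided 5% (SAP 7.2, 7.3, 9.3.1.3). The plan gives no figure for covariance parameters or per-visit error, so the only one to reproduce is its power: 3.4 / (7 × √(2/72)) − 1.96 = 2.914 − 1.960 = 0.954, and Φ(0.954) = 83.0%. This agrees with the stated minimum of 80%.

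**Assumed.** SDs by visit and between-visit correlations. The documents give neither.

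**Step 1: redundancy.** The likelihood depends only on the marginal covariance V = τ²J + R, where J is the 3×3 matrix of ones.

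- R unstructured: replacing (τ², R) by (τ² − c, R + cJ) leaves V unchanged. There are 1 + 6 = 7 parameters with rank 6.
- R compound symmetric, R = σ²[(1 − ρ)I + ρJ]: V = (τ² + σ²ρ)J + σ²(1 − ρ)I. There are 3 parameters with rank 2, so the fallback is redundant too.
- Two visits, as the SAP lists for CFQ-R and sweat chloride (Weeks 4 and 8), with R unstructured: 4 parameters with rank 3.

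In each case V itself is identified, and so are the fixed effects and their standard errors. Setting τ² = 0 gives the ordinary unstructured model.

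**Step 2: per-visit error under compound symmetry, complete data.** The fit gives every visit the mean variance, so the true error at visit j is 2 × [1 − Φ(1.96 × √(mean variance / variance at j))].

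For SDs 6/7/8, the mean variance is (36 + 49 + 64)/3 = 49.67.

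- Week 8: 1.96 × √(49.67/64) = 1.727, error 8.4%. The interval is 0.88 of its proper width.
- Week 2: 1.96 × √(49.67/36) = 2.302, error 2.1%. The interval is 1.17 times its proper width.

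For SDs 6/7/9, the mean variance is (36 + 49 + 81)/3 = 55.33. Week 8: 1.96 × √(55.33/81) = 1.620, error 10.5%.

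| Assumed SDs, Weeks 2/4/8 | Week 2 | Week 4 | Week 8 |
|---|---|---|---|
| 7/7/7 | 5.0% | 5.0% | 5.0% |
| 6.5/7/7.5 | 3.5% | 5.0% | 6.7% |
| 6/7/8 | 2.1% | 4.9% | 8.4% |
| 6/7/9 | 1.5% | 3.7% | 10.5% |
| 8/7/6 | 8.4% | 4.9% | 2.1% |

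**Step 3: the averaged contrast.** The variance of a subject's three-visit mean is the sum of all nine elements of V, divided by 9. Compound symmetry reproduces the mean variance and the mean covariance, so with complete data it estimates that sum without bias.

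**Step 4: simulation.** REML, 80 per arm, correlation 0.6, 10% dropout completely at random, 1,000 null trials per case (Monte Carlo SE about 0.7 points), no baseline covariates, and a t reference with 150 df in place of Kenward-Roger.

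| SDs | Fit | Week 2 | Week 4 | Week 8 | Average |
|---|---|---|---|---|---|
| 6/7/8 | Compound symmetry | 2.1% | 5.6% | 8.9% | 5.9% |
| 6/7/8 | Unstructured, no random effect | 5.2% | 5.6% | 6.0% | 5.5% |
| 5/7/9 | Compound symmetry | 0.4% | 4.3% | 10.9% | 4.7% |
| 5/7/9 | Unstructured, no random effect | 5.5% | 4.2% | 4.2% | 3.8% |

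A second simulation (SDs 6/7/8, correlations 0.7/0.5/0.7, 1,200 trials) gave 2.4% at Week 2, 8.2% at Week 8 and 5.3% for the average under compound symmetry. A fallback allowing visit-specific variances brought the per-visit rates back to about 5%.

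**Step 5: treatment-by-visit test.** Under compound symmetry with complete data and SDs 6/7/8 (4,000 trials), it rejected in 5.6% to 5.8% of null trials, against 5.3% to 5.8% with equal SDs of 7. Across all unequal-SD runs the range was 4.6% to 6.9%.

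**The case against.** The case for leaving the text alone has four parts.

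1. **No confirmatory result is touched.** The hierarchy tests only averages through Week 8, and those stay near 5% even under the fallback. This stands.
2. **Redundancy is not failure.** Only the split between subject variance and residual covariance is undetermined. A reader might infer that the primary model cannot be estimated. Step 1 shows otherwise. This stands.
3. **The trigger is narrow.** The SAP invokes compound symmetry only for a problem due to the unstructured matrix, and a failure caused by the extra random term is not literally that. Nothing in the documents suggests that 6 covariance parameters would be hard to estimate with 160 subjects. This stands as to likelihood. The text still does not tell a programmer to drop the random term before changing the covariance.
4. **The size is assumed.** The plan works with one common SD of 7. With equal variances the distortion is nil, and with variances falling over time Week 8 becomes conservative. This stands. A reader might infer that Week 8 is anti-conservative as a rule, but the documents do not support a direction.

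Together these points set the priority. They do not justify keeping a term that adds nothing, or a fallback that assumes equal variances when alternatives are available.

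**Conclusion.** The specification should be tidied, as a minor priority. The random subject effect is redundant with the unstructured covariance and with the compound-symmetry fallback, and it can provoke avoidable fitting problems. If the fallback is used and visit variances differ, the supportive per-visit intervals and P values are miscalibrated. Over the assumed SDs tabulated above, Week 8 error runs from 2.1% to 10.5%, and is exactly 5.0% when the SDs are equal. Kenward-Roger does not repair a misspecified covariance.

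Two stronger readings are tempting and not supported. One is that the primary P value is unsafe: complete-data algebra and simulation with random dropout both keep the averaged contrast near 5%. Dropout depending on earlier values was not simulated, so nothing is claimed about it. The other is that the treatment-by-visit test is badly wrong: unequal variances barely move it.

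**What to change.** - In SAP 9.3.1.3, delete the random subject effect and fit the unstructured covariance through the repeated-measures statement only. Correct the misprinted adjective in the same edit. The models in 9.3.2.2 and 9.3.3.2 follow.
- Replace compound symmetry with a pre-specified fallback that allows visit-specific variances, for example heterogeneous Toeplitz and then heterogeneous compound symmetry, keeping Kenward-Roger. With three visits these have 5 and 4 parameters against 6 for unstructured. The first is close to the structure that would have failed, so the second is needed in the list.
- A sandwich standard error is optional. It is needed only if plain compound symmetry is kept as a last resort, and it would then take the place of Kenward-Roger.

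The cost is a few words of SAP text before database lock. The intended primary estimate does not change.
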